## 1. INTRODUCTION

This statistical analysis plan (SAP) provides the detailed methodology for summary and statistical analyses of the data collected in Study INDV-2000-102 Part III and is based on Protocol Amendment 4/09 May 2023 (Version 5.0). This SAP supersedes the statistical considerations stated in the protocol; any differences are identified in [Appendix 2](#) of this document. However, major modifications of the primary endpoint definition or its analysis will also be reflected in a protocol amendment. Post hoc or unplanned analyses not specified in the SAP will be documented in the clinical study report (CSR).

## VERSION HISTORY

**Table 1 SAP Version History Summary**

SAP Version	SAP Finalization Date	Associated Protocol Amendment	Protocol Approval Date	Change	Rationale
1.0	04Dec2023	Amendment 4.0, Version 5.0	09May2023	Not Applicable	Original version

[figure not shown]
### 1.1. Objectives and Endpoints

Each study objective is presented in [Table 2](#) with associated estimands. Intercurrent events occur after treatment starts and either preclude the observation of an endpoint or affect its interpretation. For the intercurrent event of study discontinuation, the principal stratum strategy will be used for pharmacokinetic (PK) endpoints in that only subjects with an adequate amount of PK data will be included in the PK population; for all other endpoints, the while-on-treatment strategy will be used since data will be collected only up to end of study (EOS) or study discontinuation. Other potential intercurrent events in this study are prohibited medications and lifestyle restrictions detailed in protocol sections 9.6.2 and 9.6.3, respectively. Possible strategies for these intercurrent events are treatment policy (intervent event is ignored), while on treatment (data collected after the event is ignored), and principal stratum for PK endpoints (subject is excluded from the PK population), to be decided by the sponsor on a case-by-case basis.

[figure not shown]
**Table 2 Study Objectives and Estimands**

		Estimand		
Objective Clinical Category	Statistical Category	Variable/Endpoint	Pop-ulation	Population-Level Summary
Primary Objective				
Assess the safety and tolerability following repeated doses of INDV-2000 administered alone and with SUBOXONE sublingual (SL) film in an opioid use disorder (OUD) treatment seeking population.				
Adverse Events (AEs)	Primary	Incidence, severity, and relatedness of treatment-emergent adverse events (TEAEs), serious adverse events (SAEs) and events leading to study discontinuation or death.	Safety	Categorical descriptive

**Exploratory Objectives**

		Estimand		
Objective Clinical Category	Statistical Category	Variable/Endpoint	Pop-ulation	Population-Level Summary

[figure not shown]

		Estimand		
Objective Clinical Category	Statistical Category	Variable/Endpoint	Pop-ulation	Population-Level Summary

## 1.2. Study Design

This is a Phase I study to assess repeated doses of INDV-2000 in healthy volunteers and in treatment-seeking individuals with OUD. The study will be conducted in three parts, as depicted in [Figure 1](#). This SAP is for Part III only.

**Figure 1. Study Schematic**

Key features of the study design are described below.

- Part III is an open-label study in OUD treatment-seeking individuals.
- Part III dose determination will follow a blinded review of safety and PK data from Parts I and II.
- The screening period for Part III is up to 35 days. Subjects will receive SUBOXONE SL film during a 6-day, in-clinic run-in period. Qualifying subjects will then be enrolled into the study, consisting of a 14-day in-clinic period followed by an EOS visit on Day 21. Subjects will receive SUBOXONE SL film alone on Days 1 and 2, SUBOXONE SL film and INDV-2000 on Days 3-9, and INDV-2000 alone on Days 10-13. Total study duration per subject, from screening through the EOS visit, will be approximately 56 days.

## 2. STATISTICAL HYPOTHESES

There will be no statistical inference in this study. All statistics will be descriptive only.

## 2.1. Multiplicity Adjustment

There will be no statistical inference in this study; therefore, there will be no need for multiplicity adjustment.

## 3. SAMPLE SIZE DETERMINATION

The sample size for each part of the study is not based on formal power calculations because the study is designed to provide preliminary descriptive assessments of the safety, tolerability and PK for INDV-2000. The sample sizes used are typical for studies of this nature and should be adequate to assess the parameters described.

## 4. POPULATIONS FOR ANALYSIS

Data for all subjects will be assessed to determine if subjects meet the criteria for inclusion in each analysis population shown in [Table 3](#) prior to releasing the database and classifications will be documented per standard operating procedures.

**Table 3 Analysis Populations**

Population	Description
Screened	Subjects who signed informed consent.
Enrolled	Subjects who met Day -1 run-in assessment criteria.
Safety	Subjects who received at least one dose of investigational medicinal product (IMP). Subjects will be summarized according to the study treatment received.
Run-In Safety	Subjects who received at least one dose of study drug during the run-in period.
PK	Subjects who received at least one dose of INDV-2000, have an adequate number of PK samples collected to derive any PK parameter, and have no protocol deviations that would significantly alter plasma concentration of INDV-2000.

## 5. STATISTICAL ANALYSES

### 5.1. General Considerations

#### 5.1.1. Timing of Analyses

Database lock and final production of tables, figures, and listings (TFLs) will occur after the completion of Part III.

---

### **5.1.2. Programming Environment**

SAS® version 9.4 or higher (SAS Institute, Cary, North Carolina) will be used for statistical analyses and for the production of Study Data Tabulation Model (SDTM) and Analysis Data Model (ADaM) data sets as well as TFLs.

### **5.1.3. Reporting Conventions**

Data will be summarized by visit for visit-based assessments and by treatment for non-visit-based assessments, if applicable. TFL tables of contents, mock-ups, and specifications are provided in a separate document from the SAP. The following reporting conventions will be followed:

- Treatment group names and order in tables and figures for non-visit-based assessments, where applicable, will be SUBOXONE, INDV-2000+SUBOXONE, INDV-2000, All Subjects; some of these tables may omit the All Subjects groups. Tables and figures for visit-based assessments will only show All Subjects and will include a footnote to describe treatments administered for each visit, if applicable.
- Tables and figures will present summaries/analyses by study visit and time point, if applicable, for visit-based assessments.
- Table column headers and figure legends will include subgroup sample sizes (“N = xx”). Sample sizes reported as part of descriptive statistics (“n”) will be the number of non-missing observations.
- Listings will generally include unique subject identifier (including site identifier); treatment, if applicable, if the assessment is not visit-based; study visit/time point; assessment or collection date/time; parameter; and observed value.

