14.9.1 Treatment-Emergent Adverse Events (TEAEs)

A TEAE is defined as an AE with start date/time at or after dosing with IMP. The number and percentage of subjects reporting TEAEs will be presented for each treatment by MedDRA system organ class (SOC) and preferred term (PT), each in descending order of frequency among all subjects in the given part of the study (then alphabetically in case of ties).

Incidence and number of study drug-related TEAEs, TESAEs, study drug-related TESAEs, TEAEs leading to death, TEAEs leading to IMP discontinuation, and TEAEs leading to IMP interruption will be presented both in an overall summary table and by SOC and PT. Included in the overall summary table will be incidence and number of severe TEAEs and TEAEs with grade 3 or higher toxicity grade (applicable for Parts I and II only). TEAE incidence will also be summarized by maximum severity within SOC and PT. Incidence of TEAEs will be summarized by PT only (not SOC) in descending order of incidence among all subjects (within study part).

In summaries by severity and relationship to study drug, if more than one TEAE is coded to the same PT for the same subject, the subject will be counted only once for that PT using the most severe/most related occurrence. Missing severity, toxicity, and relatedness will be queried until resolution.

Non-TEAEs and, for Part III, run-in AEs in the Run-In Safety Population will be summarized separately.

Separate listings will be presented for TEAEs, TESAEs, TEAEs leading to IMP interruption or discontinuation and TEAEs leading to death.

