### **5.1.5. Definitions**

IMP: INDV-2000 or placebo (placebo not applicable in Part III)

---

Study Drug: INDV-2000, SUBOXONE SL film, or placebo (placebo not applicable in Part III).

Screening Period: Informed consent to Day -7 Clinic Check-In.

Run-In Period: Day -7 to Day -1 Run-In Assessment

End-of-Study (EOS): Early termination or completion of last scheduled visit.

Enrolled Subject: Met Day -1 run-in assessment criteria.

Study Day 1: day of first dose of study drug administration after the run-in period.

Study day:

- Study day = date of assessment – date of Study Day 1 + 1, for assessments on or after Study Day 1
- Study day = date of assessment – date of Study Day 1, for assessments before Study Day 1

Study time: time of assessment – time of first study drug administered in the clinical unit.

Duration:

- Duration in days = end date – start date + 1
- Duration in minutes = end time – start time. Durations will be adjusted for Daylight Saving Time, where applicable.

Baseline observation: for a given parameter for a given subject, the last observed value, including unscheduled and repeated assessments, before the first dose of IMP or planned first dose of IMP if IMP was not administered.

Run-in baseline observation: for a given parameter for a given subject, the last observed value, including unscheduled and repeated assessments, before the first dose of study drug during the run-in period.

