### **5.5.2. Adverse Events**

A TEAE is an AE that started at or after first administration of IMP. A run-in AE is an AE that started at or after first administration of study drug during the run-in period. AEs will be assigned to study treatments based on start dates and times of treatments and start dates and times of AEs.

AEs will be coded to a System Organ Class (SOC) and Preferred Term (PT) using Medical Dictionary for Regulatory Activities (MedDRA). Additional details of the coding process, including the current version of the dictionary, are described in the Data Management Plan. All AEs will be listed for individual subjects. Listings will include SOC, PT, and reported term; treatment; onset date and time, end date, and duration; run-in status, treatment-emergence, severity, toxicity grade (though not required for Part III of the study), seriousness and seriousness criteria; relationship to study drug; action taken with IMP; action taken with SUBOXONE SL film; whether concomitant treatment was given; outcome; and whether the AE resulted in study discontinuation. Duration (days) is calculated as the AE end date – the AE onset date +1; for ongoing AEs, the date of end of study participation will be used as the end date. Duration will be missing if either the start or end date is partially or completely missing. SAEs, TEAEs leading to IMP discontinuation or interruption, AEs leading to SUBOXONE SL film discontinuation or interruption, and fatal AEs will be listed separately.

The incidence and number of all TEAEs, TESAEs, study drug-related TEAEs and TESAEs, severe TEAEs, TEAEs leading to IMP discontinuation or interruption, and fatal TEAEs will be presented in an overall summary table.

TEAEs, TESAEs, study drug-related TEAEs and TESAEs, and run-in AEs will be summarized by MedDRA SOC and PT, each in descending order of frequency among all subjects within study part (then alphabetically in case of ties). TEAEs will also be

summarized by maximum severity within SOC and PT. If an AE is reported more than once by a subject within a SOC and/or PT, the maximum reported level of severity will be used at each level of summation in the severity summary table.

Incidence and number of TEAEs will also be summarized by PT only (ie, not SOC), sorted by descending frequency among all subjects (within study part).

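### Under the planned schedule a SUBOXONE column in a Part III TEAE table would be empty, AEs on SUBOXONE alone are split across other summaries, and TEAE percentages cover unequal windows without person-time

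*SAP*

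**What the plan says.** SAP 5.1.3 sets the column names and order for tables that are not visit-based: "where applicable, will be SUBOXONE, INDV-2000+SUBOXONE, INDV-2000, All Subjects". It leaves the layouts elsewhere: "TFL tables of contents, mock-ups, and specifications are provided in a separate document from the SAP".

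SAP 5.5.2 defines the primary events: "A TEAE is an AE that started at or after first administration of IMP". SAP 5.1.5 makes INDV-2000 the only IMP in Part III and treats SUBOXONE as study drug but not IMP. Columns are filled by onset: "AEs will be assigned to study treatments based on start dates and times of treatments and start dates and times of AEs". Protocol 14.9.1 asks for a by-treatment display: "The number and percentage of subjects reporting TEAEs will be presented for each treatment".

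The schedule in SAP 1.2, after a 6-day run-in on SUBOXONE, is "SUBOXONE SL film alone on Days 1 and 2, SUBOXONE SL film and INDV-2000 on Days 3-9, and INDV-2000 alone on Days 10-13", with an end-of-study visit on Day 21. Protocol 14.7.1 follows the primary endpoints from first IMP dose to final follow-up.

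For AEs before Day 3, SAP 5.5.2 summarizes run-in AEs separately. A further category combines AEs from before any study drug with AEs after run-in but before first IMP, that is, Days 1-2. Protocol 10.1.1 instead counts everything from first SUBOXONE to first INDV-2000 as a run-in AE.

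TEAEs are reported as incidence and number. No exposure-adjusted rate is specified, although SAP 5.5.1 summarizes exposure by period.

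**The concern.** The primary objective of Part III is the safety of INDV-2000 alone and with SUBOXONE. There is no concurrent control and no inference, so the descriptive AE tables are the result. Readers will compare the columns side by side.

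Three features make that comparison unsafe. A SUBOXONE column restricted to TEAEs holds nothing under the planned schedule. The AEs that belong to SUBOXONE alone are not brought together in any specified summary. The remaining columns show raw percentages over windows of different length, and one of those lengths is undefined. A difference between columns could then reflect definitions and window lengths, not the drug.

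**Working it through.** **Windows.** These are counted from SAP 1.2 and the Part III schedule in Protocol Appendix 3.

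- SUBOXONE alone: Days -6 to -1 (6 days) plus Days 1-2 (2 days) = 8 days.
- Combination: Days 3-9 = 7 days.
- INDV-2000 alone: Days 10-13 = 4 days on drug. Adding Days 14-21 (8 days, nominal) gives 4 + 8 = 12 days.

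The protocol title states INDV-2000 dosing of up to 11 days in Part III, and 7 + 4 = 11 reproduces it.

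**Empty column.** A TEAE needs onset at or after first INDV-2000, which is planned for Day 3. Scheduled SUBOXONE-alone time ends before that dose. The TEAE window inside that period is therefore 0 days, and the column shows 0% whatever the true AE rate.

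The combination column would rarely also be empty. With a daily AE probability h and 16 subjects (the planned maximum), the chance of at least one subject with a TEAE over 7 days is 1 - (1 - h)^(7 × 16). This is 89.6% at h = 2%, 99.7% at 5% and above 99.9% at 10%.

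**Split of AEs on SUBOXONE alone.** Under Protocol 10.1.1, an AE starting on Day 1 or 2 is a run-in AE. Under SAP 5.5.2 it falls in the category that is neither treatment-emergent nor run-in, together with AEs from before any study drug. SAP 6.6.5 uses yet another boundary: when the start time is missing, an AE can be classed as run-in if it ended before first IMP. The visible text of SAP Appendix 2 lists only two added populations, not this change.

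**Unequal windows.** The documents give no AE rate, so I assume the same daily probability h in every period, meaning that treatment changes nothing. Expected incidence over d days is 1 - (1 - h)^d.

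| Window | d | h = 2% | h = 5% | h = 10% |
|---|---|---|---|---|
| SUBOXONE alone, Days 1-2 only | 2 | 4.0% | 9.8% | 19.0% |
| SUBOXONE alone, Day -6 to Day 2 | 8 | 14.9% | 33.7% | 57.0% |
| INDV-2000+SUBOXONE, Days 3-9 | 7 | 13.2% | 30.2% | 52.2% |
| INDV-2000 alone, Days 10-13 | 4 | 7.8% | 18.5% | 34.4% |
| INDV-2000 alone, Days 10-21 | 12 | 21.5% | 46.0% | 71.8% |

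The SUBOXONE rows count all AEs, not TEAEs. Ratios of the combination to the other windows, for h = 2%, 5% and 10%:

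- to INDV-2000 alone over 4 days: 13.2/7.8 = 1.69, 30.2/18.5 = 1.63, 52.2/34.4 = 1.52
- to INDV-2000 alone over 12 days: 13.2/21.5 = 0.61, 30.2/46.0 = 0.66, 52.2/71.8 = 0.73
- to SUBOXONE alone over 8 days: 13.2/14.9 = 0.89, 30.2/33.7 = 0.90, 52.2/57.0 = 0.92
- to SUBOXONE alone over Days 1-2: 13.2/4.0 = 3.3, 30.2/9.8 = 3.1, 52.2/19.0 = 2.7

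Expressed per 100 subject-days at risk, the rate of first AEs is the same in every row: 2, 5 or 10.

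**The case against.** The strongest reply is that SAP 5.1.3 is a general convention. It applies only where applicable, and it also serves medications and all-AE displays, where a SUBOXONE column makes sense. The layouts are in a separate document, and no text says that a TEAE table will carry the column. Protocol 14.9.1 is generic across the three parts. This stands, so the empty column is conditional on how the convention is applied.

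A reader might infer that the layout makes adding INDV-2000 look harmful. The documents do not support that as a general result. It follows only if the empty TEAE column is shown, or if SUBOXONE alone is limited to Days 1-2. With all AEs over the full 8 days, raw incidence slightly favours the combination. Likewise, the 1.5- to 1.7-fold excess of the combination over INDV-2000 alone assumes that the latter column closes on Day 13. Nothing says so, and closing it on Day 21 reverses the direction.

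Nor can it be said that the column could never hold a TEAE. INDV-2000 might be interrupted or stopped while SUBOXONE continues; SAP 5.5.2 lists the action taken with each separately. An AE with a missing start date can also be classed as a TEAE under SAP 6.6.5, with no rule for its column.

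It is also fair that no between-column comparison is planned, that all statistics are descriptive (SAP 2), and that every AE is listed with treatment and onset. The information therefore exists. What is missing is a summary that isolates AEs on SUBOXONE alone, and a denominator that makes the periods comparable.

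**Conclusion.** The point holds as a weakness of the primary descriptive display, not as a biased test. If the SAP 5.1.3 columns are used in TEAE tables, the SUBOXONE column is empty under the planned schedule. If the column is dropped, those tables have no SUBOXONE-alone figures, and the other summaries do not bring them together. The SAP and protocol disagree on whether Day 1-2 AEs are run-in AEs.

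Raw percentages can differ between columns with no true difference, in either direction. Under an equal daily probability of 2% to 10%, the ratio of the combination to INDV-2000 alone runs from 1.5-1.7 (4-day window) to 0.6-0.7 (12-day window). These sizes rest on an assumed constant daily probability, equal across periods, and on full follow-up. The empty column and the missing Day 14-21 rule rest on the documents alone.

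**What to change.** In SAP 5.5.2:

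1. Omit the SUBOXONE column from TEAE-only tables, or footnote it as empty by definition under the planned schedule.
2. Add one descriptive all-AE table by period: SUBOXONE alone (first run-in dose to first INDV-2000), INDV-2000+SUBOXONE (Days 3-9), INDV-2000 alone (Days 10-13), and post-treatment follow-up (Day 14 to end of study) as its own column. In each, give subjects at risk, subject-days, and events per 100 subject-days beside the percentage.
3. Show the SUBOXONE-alone column for both the Run-In Safety and the Safety Populations. Note that the Safety Population excludes run-in failures, so using it alone could understate AEs on SUBOXONE.
4. Align the SAP run-in AE definition with Protocol 10.1.1, or list the change in Appendix 2.

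The cost is SAP wording and one table from data already collected. The rates assume a roughly constant hazard within each period. They cannot separate drug from period effects, such as induction during run-in or withdrawal after SUBOXONE stops, so they should stay descriptive.

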### **5.1.4. General Analysis Conventions**

Categorical variables will be summarized using frequencies and percentages. Percentages will be reported to one decimal place.

Continuous variables will be summarized using descriptive statistics (e.g., n, mean, standard deviation (SD), distribution percentiles, range). The number of decimal places for minimums and maximums will be the same as the source data. The number of decimal places for means, medians, and interquartile ranges will be the same as the source data plus one, and the number of decimal places for measures of variance will be the same as the source data plus two. See [Section 6.5 \(Appendix 5\)](#) for summary statistics and precision specifications for PK data.

Data with qualifiers (e.g., “<”) will be listed with but summarized without the qualifier.

### **5.1.5. Definitions**

IMP: INDV-2000 or placebo (placebo not applicable in Part III)

---

Study Drug: INDV-2000, SUBOXONE SL film, or placebo (placebo not applicable in Part III).

Screening Period: Informed consent to Day -7 Clinic Check-In.

Run-In Period: Day -7 to Day -1 Run-In Assessment

End-of-Study (EOS): Early termination or completion of last scheduled visit.

Enrolled Subject: Met Day -1 run-in assessment criteria.

Study Day 1: day of first dose of study drug administration after the run-in period.

Study day:

- Study day = date of assessment – date of Study Day 1 + 1, for assessments on or after Study Day 1
- Study day = date of assessment – date of Study Day 1, for assessments before Study Day 1

Study time: time of assessment – time of first study drug administered in the clinical unit.

Duration:

- Duration in days = end date – start date + 1
- Duration in minutes = end time – start time. Durations will be adjusted for Daylight Saving Time, where applicable.

Baseline observation: for a given parameter for a given subject, the last observed value, including unscheduled and repeated assessments, before the first dose of IMP or planned first dose of IMP if IMP was not administered.

Run-in baseline observation: for a given parameter for a given subject, the last observed value, including unscheduled and repeated assessments, before the first dose of study drug during the run-in period.

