5.4 Check-In and Run-In Assessment Criteria

Upon passing screening and meeting inclusion and not meeting exclusion criteria, the subject will present to the clinic for admission.

For Part I and Part II, the following criteria must be met at Day -1 for the healthy volunteer to be checked into the clinic:

- 1. Females must have a negative urine pregnancy test.
- 2. Must not have a QTcF >450 msec for males and >470 msec for females.
- 3. Must have a negative result obtained from the urine drug screen (UDS) and the alcohol test (urine ethanol).
 - a. Healthy volunteers who have a positive result for alcohol will be asked to refrain from alcohol and return the next day for retest. This may only occur once.
- 4. Must have a negative polymerase chain reaction (PCR) test result for COVID-19.

Confidential Page 32 of 108

If any of these criteria are not met, the subject will not be enrolled into the study.

For Part III, subjects must meet the following criteria in order to be checked into the clinic on Day -6:

- 1. Females must have a negative urine pregnancy test.
- 2. Must have a negative PCR test result for COVID-19.

For Part III, subjects must meet the following criteria in order to complete run-in, and proceed into the study on Day -1:

- 1. Tolerating daily dose of SUBOXONE SL film between 8mg/2mg 24mg/6mg (inclusive).
- 2. COWS score of ≤ 12 .

If any of these criteria are not met, the subject will not be enrolled.

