9.6 Prior and Concomitant Therapies

Therapies and medications will be collected from screening until the EOS visit or the ET visit, at the time points listed Section 22.1, Appendix 1, Section 22.2, Appendix 2 and Section 22.3, Appendix 3. Any concomitant medications (including herbal preparations) taken during the study will be recorded in the source documents and in the eCRF. Any changes in concomitant therapy and medications during the study will be documented, including cessation of therapy and medication, initiation of therapy and medication and dose changes.

Prior therapies and medications are considered any medication ended prior to first dose of study drug. Therapies and medications are considered concomitant if taken after dosing with IMP.

For Part III, therapies and medications taken after study drug but prior to IMP are considered run-in therapies and medications.

Any changes to concomitant therapies and medications that are not listed as permitted concomitant therapies and medications must be discussed with the study Medical Monitor.

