### **5.6.3. Prior and Concomitant Medications and Therapies**

Medications and therapies will be collected from screening through EOS and will be coded using Anatomical Therapeutic Chemical (ATC) classification codes via the World Health Organization Drug Dictionary (WHO-DD). Additional details of the coding process, including the current version of the dictionary, are described in the Data Management Plan. Prior medications and therapies will be medications/therapies that ended before first administration of study drug or were taken by subjects who did not take study drug. Therapies and medications that were started or were ongoing during run-in will be considered run-in therapies and medications. Therapies and medications that were started or were ongoing post run-in will be considered concomitant therapies and medications. A therapy or medication can be both run-in and concomitant. Therapies/medications will be assigned to study treatments based on start dates and times of treatments and start and end dates and times of therapies/medications.

Prior concomitant medications and therapies will be summarized for all subjects. Run-in medications and therapies will be summarized for the run-in safety population. Concomitant medications and therapies will be summarized for the safety population. The summary of incidence (number and percentage of subjects reporting the medication/therapy at least once) will be sorted alphabetically by therapeutic class (ATC level 2) and standardized medication/therapy name.

See Section [6.6.4 \(Appendix 6\)](#) for details on handling missing information on medications and therapies.

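### SAP 5.1.5 starts run-in on Day -7, one day before the protocol's check-in and first SUBOXONE film, so a narrow set of medications is classed as both prior and run-in

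*SAP*

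**What the plan says.** **Period definitions.** SAP 5.1.5 closes screening and opens run-in on the same day: "Screening Period: Informed consent to Day -7 Clinic Check-In", then "Run-In Period: Day -7 to Day -1 Run-In Assessment".

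**Length of run-in.** SAP 1.2 says: "Subjects will receive SUBOXONE SL film during a 6-day, in-clinic run-in period". Protocol 4.1 also gives six days of daily film.

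**Calendar in the protocol.** Part III subjects must meet criteria "in order to be checked into the clinic on Day -6" (protocol 5.4). The schedule in protocol 22.3.1 labels the screening column Days -35 to -7. It marks admission to the unit on Day -6 and film administration on each of Days -6 to -1.

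**Medication classes.** SAP 5.6.3 calls a medication prior if it ended before the first administration of study drug, a term that includes SUBOXONE film. For run-in it uses the period instead: "Therapies and medications that were started or were ongoing during run-in will be considered run-in therapies and medications". SAP 6.6.6 uses the start of run-in when end dates or times are incomplete. Protocol 9.6 ties both classes to dosing; its run-in rule is "For Part III, therapies and medications taken after study drug but prior to IMP are considered run-in therapies and medications".

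**The concern.** The SAP disagrees with itself (5.1.5 against 1.2) and with the protocol on when run-in starts. By itself that would be an editorial matter. It has an effect because 5.6.3 uses two different reference points: the first dose for prior medications and the period for run-in medications. If the period starts before the dose, anything that ended in between falls into both classes.

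The run-in medication table should describe what subjects took once SUBOXONE had started. As defined, it can also include medication taken before any study drug, and the same records appear in the prior table. The SAP's introduction says that it supersedes the protocol's statistical considerations, so a programmer who follows it literally would apply the 5.1.5 definition rather than protocol 9.6.

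This point concerns the start of run-in, not its end.

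**Working it through.** **1. Reproduce the stated length.** The SAP's rule for days before Day 1 is "Study day = date of assessment – date of Study Day 1, for assessments before Study Day 1", so there is no Day 0 and the day before Day 1 is Day -1. The number of days from Day -a to Day -b is a - b + 1.

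- Protocol bounds, Day -6 to Day -1: 6 - 1 + 1 = 6 days. This reproduces the figure in SAP 1.2 and protocol 4.1.
- SAP 5.1.5 bounds, Day -7 to Day -1: 7 - 1 + 1 = 7 days. This does not.

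The excess is one day, or 1/6 = 17% of the stated length.

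**2. Apply the SAP 5.6.3 rules to test records.** Assumptions: the first film is given at 09:00 on Day -6, and Day -7 counts from the start of the calendar day, since the protocol has no check-in on that day to supply a clock time. A record is prior if it ended before the first film. It is run-in if any part of it falls inside the run-in period. The last three columns vary only the start of that period.

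| Medication | Prior? | Run-in if period starts Day -7 (SAP 5.1.5) | Run-in if it starts at the beginning of Day -6 | Run-in if it starts at first film |
|---|---|---|---|---|
| Ended Day -10 | yes | no | no | no |
| Taken only on Day -7, 12:00 | yes | **yes** | no | no |
| Ended Day -6, 06:00 | yes | **yes** | **yes** | no |
| Continued past first film, ended Day -3 | no | yes | yes | yes |

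Bold marks records that are both prior and run-in. The SAP text produces two. Changing the day to -6 leaves one. Starting at the first film leaves none.

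**3. Missing end time (SAP 6.6.6).** Take a medication known to have started earlier, with end date Day -7 and no end time. The end date is on or after the SAP's run-in start date, so the rule makes it run-in. Yet the date alone shows that it ended before the Day -6 film, so 5.6.3 also makes it prior. The overlap therefore carries into the missing-data rule.

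**4. Compare with protocol 9.6 and the AE rule.** Under protocol 9.6, both bold records are prior only, because neither was taken after study drug. SAP 5.5.2 likewise starts run-in AEs at the first administration of study drug. So an event on Day -7 would be a non-run-in AE, while a medication taken for it that day would be a run-in medication.

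**The case against.** The strongest reply is that this is a one-day slip in a descriptive study. Few medications will have ended in so short an interval, the prior and run-in summaries are separate tables on different populations and are never added, and changing -7 to -6 restores agreement with SAP 1.2 and the protocol. The SAP also does not expressly forbid overlap between prior and run-in; it says only that a medication may be both run-in and concomitant.

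Most of that stands. No total is inflated and the set of records is narrow. Two parts do not stand. The overlap departs from protocol 9.6, and the legible rows of SAP Appendix 2 do not list it as a change (weak evidence, since that table may be incomplete). Changing the day alone also leaves the hours on Day -6 before the first film.

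A reader might infer more, but the documents do not support it:

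- **That prior medications in general are doubly classed.** A medication that ended before Day -7 is prior only.
- **That screening readings on Day -7 enter run-in summaries.** SAP 6.3 applies no windowing and uses the visit recorded in the CRF, so such a reading stays under its CRF visit.
- **That Study time, anchored to the "time of first study drug administered in the clinical unit", distorts results.** No legible output uses it, and the PK and PD derivations are not visible.
- **That the stated duration of about 56 days is wrong.** Days -35 to 21 with no Day 0 give 35 + 21 = 56. Screening is a maximum and the total is approximate.

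**Conclusion.** The point holds as a minor correction. The run-in start in SAP 5.1.5 is inconsistent with SAP 1.2, protocol 5.4 and the protocol 22.3.1 schedule. The effect is limited to medications that ended on Day -7, or on Day -6 before the first film. These are classed as prior and run-in where the protocol makes them prior only.

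The documents do not allow a count of such records. For scale only, one subject in a denominator of 16, the planned Part III maximum, is 1/16 = 6.3 percentage points. The Run-In Safety Population, on which the run-in medication table is based, may be larger because run-in failures who took film belong to it.

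Run-in AEs, the run-in baseline, the IMP baseline and the Safety Population are tied to dosing. The Run-In Safety Population is the same whether run-in is said to start on Day -7 or Day -6, because no film is scheduled on Day -7. The primary TEAE endpoint is untouched.

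The conclusion assumes that 5.6.3 is programmed from the 5.1.5 definition, and that medications are collected from screening, as SAP 5.6.3 and protocol 9.6 say. The 22.3.1 table marks concomitant medication assessment only from Day -6, so the number of Day -7 records depends on what is entered retrospectively.

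**What to change.** 1. In SAP 5.1.5, reconcile the check-in day with protocol 5.4 and the 22.3.1 schedule.
2. Define the Screening Period as running from informed consent to just before the first run-in SUBOXONE dose, and the Run-In Period as starting at the actual date and time of that dose. SAP 5.5.2 already uses this start for run-in AEs.
3. Use that start in 5.6.3 and 6.6.6, and state that prior and run-in are mutually exclusive. For an end date equal to the date of the first film with no end time, 6.6.6 would still assign run-in; say that such a record is then not also prior.

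The cost is SAP wording and the matching programming specification, before database lock. No new data are needed: protocol 9.7 already has the time of each in-clinic dose recorded.
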